5.3.4 Recording of Daily Intake Dose

To track the daily intake of study tablets, study participant will be required to keep a diary to record the number of tablet taken and the times of the day when the test tablets are taken (See Appendix 7. Log Form for Daily Intake of Test Tablets).

5.3.4 Criteria for Removal from Study

Given the absence of dose-limiting toxicities described in prior clinical trials, clinically significant toxicity is not expected from exposure to Avmacol® tablets. However, if a participant shows symptoms or signs of Grade ≥ 2 toxicity attributable to Avmacol®, the participant will be withdrawn from the trial and the study supplement will be discontinued. Follow-up will be maintained until the abnormality is resolved.

Participants maintain the right to leave the trial of their own volition at any point.

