5.5 Clinical Visits

Besides two clinical visits in stage 1 of the study for eligibility screening, all eligibility study participants will begin taking the study tablets at visit 1 of stage 2 of the study and return to the study clinic at the end of months 3, 6, 9, and 12 (the end of treatment period). At each clinical visit, the clinical research nurse/assistant will conduct the following:

- 1) Exam the subject's diary for dosing and timing of intake of test tablets, and keep the diary in subject's folder.
- 2) Count and record the remaining tablets given.
- 3) Provide new study tablets that will supply the next 3 months.
- 4) Study participant will turn in the self-administered questionnaire for recording his/her intake of cruciferous vegetables in the past 3 months using a dietary frequency questionnaire (Appendix 5).
- 5) Collect blood, spot urine and nasal brushing samples
- 6) Conduct pulmonary function test: FEV1/FVC
- 7) Collect safety and toxicity measures at each clinical visit (once every 3 months) during the 12-month treatment period:
 - a) Collect adverse events (AEs) using the AE Recording Form (Appendix 8)

- b) Conduct physical examination including body weigh, height, and vitals by a registered nurse and record the results in the patient's study file
- c) Laboratory evaluation: CBC with platelets and differential, chemistry panel including liver function testing.
- 8) Only at the end of treatment period, bronchoscopy will be performed on the patient using the same procedure as described above in 5.1(8) and bronchial biopsies and lavage samples collected (stage 2- visit 5).

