5.6 Withdrawal from the Protocol

- 1) Unacceptable toxicity
- 2) Development of cancer
- 3) Patient refusal
- 4) Noncompliance
- 5) Death

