5.7 Off Study Date

The “Off Study” date will be the date of the last clinical visit, i.e., stage 2 – visit 6 after the second bronchoscopy. If the patient withdraws from the study earlier, but agrees to the post-treatment follow-up, they will be contacted via telephone one month after the original off-study date.

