9.1 Statistical Analysis for histological responses

Endobronchial histology scores will be first summarized within each bronchoscopy by using 3 separate endpoint measures pre and post treatment respectively: 1) dysplasia index (DI, number of biopsies with dysplasia/total number of biopsies x 100), 2) average of all histological scores (all biopsies scores/number of biopsies), and 3) worst biopsy score. The 3 summary end points will be analyzed within 4 different biopsy site groupings: all biopsies, biopsies from the 6 standard endobronchial sites only, site-matched biopsies from both bronchoscopies, and site-matched biopsies where the baseline biopsy is non-normal. For each patient, the mean of each of endpoints separately for each of biopsy site groupings pre and post treatment are then calculated. The primary endpoint is the dysplasia index (DI), which has a binomial distribution with at least 6 “trials” (i.e., 6 predetermined biopsy sites), and will be analyzed by generalized estimating equations (GEE) that constrains average baseline DI to be the same for both treatment and placebo groups, and tests whether average follow-up DI differs between the SF treatment and placebo groups. All other endpoints and biopsy site groupings are secondary endpoints. The primary analysis for the average and worst dysplasia scores will be a linear regression that assesses the difference in post-treatment scores by the two treatment groups, controlling for the same scores at pre-treatment. This analysis of covariance (ANCOVA) approach has optimal efficiency in a study design to assess the pre- and post-treatment measures with high within-subject correlation due to repeated measures (80). No interim analyses for futility or superiority will be performed, other than ongoing safety monitoring.

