Sample size consideration. In the iloprost trial, 57 former smokers were randomized to receive oral iloprost or placebo for 6 months. Treatment effects (adjusted for baseline levels) were statistically significant ($P \leq 0.01$) for all 3 endpoints (dysplasia index, average dysplasia score, worst dysplasia score). Anticipating a 20% dropout rate over 12 months, we will randomize at least 72 study subjects to ensure that 60 subjects complete our SF study. Assuming an average baseline dysplasia index of 22% and post-therapy 11% for subjects receiving SF, a simulation with 10,000 trials with a sample size of 60 subjects has yielded an 80% statistical power to detect a statistically significant (two-sided $p < 0.05$) treatment effect, using generalized linear models (binomial family, 6 biopsies) after controlling for baseline levels of DI. Calculations are similar for other endpoints, and actual power should be greater than the DI measure because they are continuous measures and have observed within-subject correlation (i.e., repeated measures).

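### Stopping tablets for toxicity or noncompliance counts as leaving the trial, so the month-12 bronchoscopy and the primary endpoint are lost for reasons that treatment can affect

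*Combined protocol and SAP*

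**What the plan says.** All references are to the combined protocol and SAP.

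- **Removal.** Under 5.3.4 Criteria for Removal from Study, after Grade 2 or higher toxicity attributed to the supplement, "the participant will be withdrawn from the trial and the study supplement will be discontinued". What continues is safety follow-up: "Follow-up will be maintained until the abnormality is resolved". Section 5.6 lists "Noncompliance" among the reasons for withdrawal from the protocol, with no threshold. Section 5.4 allows no dose modification.
- **After removal.** Section 5.7 provides: "If the patient withdraws from the study earlier, but agrees to the post-treatment follow-up, they will be contacted via telephone". Section 5.8 adds annual mailed questionnaires.
- **Endpoint collection.** Section 5.5, item 8: "Only at the end of treatment period, bronchoscopy will be performed on the patient". Section 5.5 puts the end of treatment at month 12, and the calendar in Section 6 has no early-termination visit.
- **Analysis.** Section 9.1 makes the dysplasia index (DI) the primary endpoint. It uses a GEE that constrains baseline DI to be equal across arms and "tests whether average follow-up DI differs between the SF treatment and placebo groups". It names no analysis population and no handling of a missing follow-up DI. Dropout enters only as a count: "Anticipating a 20% dropout rate over 12 months", at least 72 are randomised so that 60 complete.

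**The concern.** Stopping tablets and leaving the study are treated as one event. Refusal and death cannot be avoided by design. Removal for toxicity or noncompliance is the protocol's own rule, and it ends collection of the primary endpoint in people who might gladly have returned.

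Both triggers occur after randomisation, and treatment can affect both. If they fall unequally on the arms, and those removed differ in dysplasia from those who stay, the comparison in 9.1 can show a difference with no drug effect, or misstate a real one. Even without bias, the result describes participants who were not withdrawn rather than everyone randomised.

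**Working it through.** **1. What happens to a willing participant who stops tablets.** Sections 5.3.4 and 5.6 take the participant off the trial. The only later bronchoscopy is tied to the end of the treatment period (5.5). Sections 5.7 and 5.8 offer a telephone call and mail, neither of which can yield a DI. Section 5.1, item 8, mentions re-biopsy at the end of the study period but does not extend it to people already withdrawn. So no follow-up DI is planned. The consent form is not in the public text and may say more.

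**2. The plan's own power figure.** Inputs from 9.1: DI 22% at baseline, 11% after SF, 6 biopsies, 60 completers, two-sided 0.05, stated power 80%. Assuming placebo stays at 22% and biopsies are independent, 30 × 6 = 180 biopsies per arm gives 80.5% power. A simulated binomial model adjusted for baseline DI (4,000 runs) gives 79.8%. The figure reproduces, and it is a figure for completers.

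**3. How many lack a follow-up DI, from all causes.** 72 − 60 = 12 (16.7%), or 0.20 × 72 = 14.4. These counts include refusal, cancer and death. The share due to toxicity or noncompliance is not given, so the recoverable number lies anywhere from 0 to about 14.

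**4. Bias with no drug effect (hypothetical, unadjusted for baseline).** Let a and p be the leavers among 36 per arm (SF, placebo), and δ the leavers' follow-up DI minus their arm's mean. Those remaining average δ × a/(36 − a) below the SF arm mean, and likewise for placebo, so

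bias = δ × [a/(36 − a) − p/(36 − p)].

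Take δ = 11 points, an assumption that merely reuses the size of the planned effect, and 14 leavers:

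- 7 v 7: 0
- 9 v 5: 11 × (9/27 − 5/31) = 11 × 0.172 = 1.9 points
- 10 v 4: 11 × (10/26 − 4/32) = 11 × 0.260 = 2.9 points

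At δ = 5.5 these halve. If the leavers' excess is already present at baseline, linear adjustment leaves roughly (1 − r) of the bias, with r the within-subject correlation. At an assumed r of 0.5, 1.9 and 2.9 become about 0.9 and 1.4.

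**5. Dilution if leavers are included.** Difference in all randomised = 11 × [(1 − d) + d × b], with d the share leaving and b their share of the benefit (assumed).

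- b = 1: 11 points
- b = 0.5: 10.1 (d = 12/72) or 9.9 (d = 0.20)
- b = 0: 9.2 or 8.8

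**6. Power bounds.** By normal approximation, 80% at 30 per arm for 11 points implies SE = 11/2.80 = 3.93 and SD = 3.93 × √(30/2) = 15.2. At 36 per arm, SE = 15.2 × √(2/36) = 3.58. Power is then about 87% for 11 points, 73% for 9.17 and 69% for 8.8. These figures assume that every dropout is recovered, which cannot happen.

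**The case against.** The strongest case against has four parts.

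- **The model may already help.** Section 9.1 constrains baseline DI, and such a GEE can retain participants who have only a baseline value. This stands in part. Section 9.1 does not say that it will retain them, and unweighted GEE still needs data missing completely at random, which removal for toxicity or noncompliance makes doubtful.
- **Toxicity and imbalance may be small.** Section 4.1.7 reports no Grade 2 or higher toxicity at this dose and expects the formulation to mask taste. The burden of eight tablets a day is the same in both arms. Table 3 shows near balance in placebo-controlled data: AEs in 8/27 v 9/27 in one trial, and Grade 1 events in 6 v 4 participants in another. On the other side, 4.1.6.2 reports that 2 of 50 dropped out for nausea or bitter taste on a 150 µmol SF beverage. The objection stands as a limit on size: the number affected may be few.
- **An on-treatment emphasis is defensible** in a proof-of-principle phase 2 study whose aim is the effect of 12 months of daily dosing. That is a legitimate choice, but 9.1 does not make it.
- **The scenarios are invented.** Correct. Neither δ nor the unequal splits come from the documents.

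A reader might infer that the 9.1 comparison covers only people who took their tablets. The documents do not support that: 5.6 sets no adherence threshold, so poor adherers who are not withdrawn reach month 12 and are biopsied. A reader might also infer that this rule costs the trial all 12 to 14 dropouts. It does not, because that count is for all causes.

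**Conclusion.** The point holds as a design weakness that is cheap to repair. Followed as written, the plan stops collecting the primary endpoint after events that treatment can affect, and the comparison in 9.1 is limited to participants not withdrawn.

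Its size is unknown. The number affected is some part of 12 to 14 and may be small. Bias is zero if leaving is balanced and leavers differ from stayers to the same extent in both arms. It reaches about 2 to 3 points only under assumed splits of 9 v 5 or 10 v 4 with an assumed 11-point difference in leavers, before baseline adjustment; it is less afterwards if that difference already exists at baseline. A claim that the trial's result will be biased by that amount would go beyond the documents. The silence of 9.1 on analysis set and missing DI would, taken alone, be only missing detail; it matters here because the removal rule generates the missing values.

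**What to change.** - **5.3.4 and 5.6:** separate stopping tablets from leaving the study.
- **5.5, 5.7 and Section 6:** offer the month-12 bronchoscopy already scheduled to anyone who has stopped tablets, still consents and is medically fit.
- **9.1:** analyse all participants with a follow-up DI by randomised arm, state how a missing DI is handled, and add a sensitivity analysis that varies the assumed DI of those still missing, separately by arm. Report reasons for leaving by arm.

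The cost is a protocol and consent amendment and at most 12 to 14 procedures, all within the two per participant already planned. Each is invasive and comes after tablets have stopped, in people with airflow obstruction or emphysema, so it must be optional. Section 7.1.2.1 cites serious complications below 0.05%. If those recovered get no benefit, the measured effect is diluted. The bounds in step 6, about 87% power with full benefit and 69 to 73% with none, assume every dropout returns.

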5.4 Dosing Delays/Dose Modifications

There are no plans for a dose modification in the study.

5.5 Clinical Visits

Besides two clinical visits in stage 1 of the study for eligibility screening, all eligibility study participants will begin taking the study tablets at visit 1 of stage 2 of the study and return to the study clinic at the end of months 3, 6, 9, and 12 (the end of treatment period). At each clinical visit, the clinical research nurse/assistant will conduct the following:

- 1) Exam the subject's diary for dosing and timing of intake of test tablets, and keep the diary in subject's folder.
- 2) Count and record the remaining tablets given.
- 3) Provide new study tablets that will supply the next 3 months.
- 4) Study participant will turn in the self-administered questionnaire for recording his/her intake of cruciferous vegetables in the past 3 months using a dietary frequency questionnaire (Appendix 5).
- 5) Collect blood, spot urine and nasal brushing samples
- 6) Conduct pulmonary function test: FEV1/FVC
- 7) Collect safety and toxicity measures at each clinical visit (once every 3 months) during the 12-month treatment period:
 - a) Collect adverse events (AEs) using the AE Recording Form (Appendix 8)

- b) Conduct physical examination including body weigh, height, and vitals by a registered nurse and record the results in the patient's study file
- c) Laboratory evaluation: CBC with platelets and differential, chemistry panel including liver function testing.
- 8) Only at the end of treatment period, bronchoscopy will be performed on the patient using the same procedure as described above in 5.1(8) and bronchial biopsies and lavage samples collected (stage 2- visit 5).

5.6 Withdrawal from the Protocol

- 1) Unacceptable toxicity
- 2) Development of cancer
- 3) Patient refusal
- 4) Noncompliance
- 5) Death

5.7 Off Study Date

The “Off Study” date will be the date of the last clinical visit, i.e., stage 2 – visit 6 after the second bronchoscopy. If the patient withdraws from the study earlier, but agrees to the post-treatment follow-up, they will be contacted via telephone one month after the original off-study date.

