3.1 Eligibility Criteria

- 1) Man or woman 55-74 years of age.
- 2) Patients with normal endobronchial biopsy findings or pre-cancerous lesions at baseline will be eligible for the study. Pre-cancerous lesions include (a) reserve cell hyperplasia, (b) squamous metaplasia, (c) mild dysplasia, (d) moderate dysplasia, and (e) severe dysplasia.
- 2) A former smoker who has a history of smoking with ≥ 30 pack-years, quits smoking within the past 10 years, and has more than 1 year sustained abstinence from smoking.
- 3) Female subjects must be of non-child bearing potential or must have a negative urine pregnancy test at screening (within 72 hours of first dose of study medication) if of childbearing potential.
- 4) Male and female subjects of childbearing potential must be willing to use adequate barrier methods of contraception from the time starting with the screening visit through 30 days after the last dose of study therapy.
- 5) Abstinence is acceptable if this is the established and preferred contraception for the subject.
- 6) Generally healthy with liver enzyme and blood count values within the ranges shown below on the blood sample drawn at the baseline screening visit.
Specifically:

White blood cells	$\geq 3,000/\text{mL}$
Total bilirubin	$\leq 1.5 \times \text{ULN}$ (upper limits of normal)
AST (SGOT)/ALT (SGPT)	$\leq 2.5 \times \text{ULN}$
BUN and serum creatinine	$\leq 1.5 \times \text{ULN}$
- 7) The presence of airflow obstruction on spirometry (GOLD 1-4 & $\text{FEV1}/\text{FVC} < 0.7$ & $\text{FEV1} < 0.8$) COPD; and/or any emphysema on CT scan.
- 8) Participants must have a Southwest Oncology Group (SWOG) performance status of 0-2 (Appendix 10).
- 9) Participants must be able and willing to undergo a bronchoscopy before and after treatment for 12 months.
- 10) Patients must be fully informed of the investigational nature of this study and must sign an informed consent in accordance with institutional and regulatory guidelines.

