5.8 Post-Treatment Follow-Up

- 1) Study participants will be contacted by telephone at the end of first month post-treatment for general health
- 2) All study participants will have routine follow-up as we do for the PluSS study participants through mails on an annual basis, to fill out a follow-up questionnaire for the diagnosis of lung cancer or any other cancer or vital status (filled out by the next-of-the-kin).

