6. STUDY CALENDAR

		Stage 1		Stage 2 (after randomization)						Post-treatment		
		Pre-clinical	#1	#1	#2	#2	#3	#4	#5	#6	Phone	Mail
Clinical visit	Targeted Date			Day 0*	Day 90±14	Day 180±14	Day 270±14	Day 360±14	Day 367±10		1 mo. after	1 yr. after
Eligibility Screening Form	Phone Interview											
MAIL OUT FORMS												
Locator Form	(mail)	(Rec)										
Baseline Questionnaire	(mail)	(Rec)						(mail)		(Rec)		
Cruciferous Vegetable intake form (compliance)					X	X	X	X		X		
SIGN CONSENT FORM	(PluSS PID)	X										
Assign subject ID (SF-Seq #)†		SF-001 SF-002 ...										
PHYSICAL EXAM												
Vitals, weight & height		X			X	X	X	X		X		
CO test		X			X	X	X	X		X		
O2 test		X										
Spirometry (PFT)		X			X	X	X	X		X		
Urinary Pregnancy Test		X										
BLOOD (for Screening or AE Monitoring)												
CBC/platelets		X				X	X	X		X		
Chemistry panel & LFT		X				X	X	X		X		
BRONCHOSCOPY												
Bronchial biopsy			X							X		
Bronchial brushing			X							X		
Bronchoalveolar lavage			X							X		
INCLUSION/EXCLUSION FORM	(X)	(X)	(X)									
TREATMENT ASSIGNMENT (TA-Seq #)‡				TA-001 TA-002 ...								
Provide study tablets (for 3 months)				X	X	X	X					
Pill count in returned bottles					X	X	X			X		
RESEARCH SAMPLES												
Blood					X	X	X	X		X		
Nasal brushing					X	X	X	X		X		
Spot urine					X	X	X	X		X		
AE ASSESSMENT FORM					X	X	X	X		X		
COMPENSATION		\$50	\$500	\$50	\$50	\$50	\$50	\$500	\$500			
Provide parking ticket		X	X	X	X	X	X	X	X			
FOLLOW-UP											X	X
General health											X	X
Lung cancer											X	X
Any cancer											X	X

* Day 0 is when the subject is given a treatment assignment number.

† Study subject ID is assigned right after the consent form is signed by a potential eligible subject. This number will be used for the entire study and all forms and sample collection sheets.

‡ Treatment assignment number is TA-sequential # of subjects entering into stage 2 of the study. the TA # randomly determines the subject's treatment arm..

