7.1.2 Risks Associated with Study Procedures

7.1.2.1 Bronchoscopy

Bronchoscopy is very safe, but no procedure is entirely free of potential risk. The following is a description of the risks of the procedure. In recent publications, the incidence of serious complications was less than 0.05% (5 in 10,000) in over 23,000 bronchoscopies. Local discomfort (coughing, gagging and soreness of your nose and throat) are frequently unavoidable but can be greatly diminished with adequate anesthesia. Bronchitis is common after bronchoscopy and may resolve spontaneously or with antibiotic treatment. Nosebleed, wheezing (about 1% chance), a decrease in blood oxygen content of approximately 10% for approximately one half hour, low grade fever (less than a 5% chance), and lung infection (pneumonia) in less than 0.1% and slight expectoration of small flecks of blood for 24 hours after the procedure (as a result of minor trauma to the bronchial lining) may occur. More serious complications such as major bleeding, lung collapse, vocal cord and bronchial spasm, and cardiac irregularity have been reported but are very rare. Since the patient will be medicated for this procedure they will need to make arrangements for someone to drive them home.

A Bronchoscopy Patient Communication Log Form is attached (Appendix 9) to follow-up the patients after the bronchoscopy is performed. Patients are called within 24 hrs., 72 hrs., and instructed to call within 30 days, if febrile, or with increased sputum production, or increasing shortness of breath or any perceived deterioration of respiratory condition.

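### Sections 5.7 and 5.8 time the post-treatment call to early stoppers from different dates, and neither that call nor an early-termination visit collects adverse events

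*Combined protocol and SAP*

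**What the plan says.** **Timing of the call.** Section 5.7 defines the off-study date as the last clinic visit, stage 2 "visit 6 after the second bronchoscopy". For those who leave sooner, it says: "If the patient withdraws from the study earlier, but agrees to the post-treatment follow-up, they will be contacted via telephone one month after the original" (the noun that follows is the off-study date). Section 5.8 states a different rule, with no exception for early leavers: "Study participants will be contacted by telephone at the end of first month post-treatment for general health". The study calendar lists the phone contact as one month after, under a post-treatment heading. Nothing says what *original* refers to.

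**Collection of AEs.** Section 5.5 has AEs recorded at the three-monthly clinic visits within the 12 months of treatment. Section 9.4 analyses them at each visit and summed over 4 time points of that period. Section 7.4 takes the DSMB's AE data from the AE Recording Form (Appendix 8). In the calendar, the row "AE ASSESSMENT FORM" carries no mark under the phone or mail contacts, which cover general health, lung cancer and any cancer.

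**Other contacts.** After bronchoscopy, section 7.1.2.1 says: "Patients are called within 24 hrs., 72 hrs., and instructed to call within 30 days, if febrile, or with increased sputum production". Section 5.3.4 (Criteria for Removal from Study) continues follow-up to resolution after removal for Grade 2 or higher toxicity attributed to the tablets. Section 7.3 requires IRB reports of associated, serious and unexpected events, with no end date.

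**The concern.** Two rules for one call cannot both be followed for a participant who stops early, unless the ambiguous word in section 5.7 happens to make them agree. Site staff would have to guess.

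The second matter is what gets recorded. Safety is a stated aim (item 1.1.4, listed under Secondary Aims), and AEs are compared between arms in only 72 people. Someone who leaves between visits, perhaps because of a mild symptom that falls short of the removal rule, has no further scheduled occasion on which the AE form is completed. The same holds for anyone with an event shortly after the last tablet or after the second bronchoscopy, once the last form is done. Such events can be absent from the section 9.4 tables even when the plan is followed exactly.

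**Working it through.** The plan states no figure for this point, so there is none to reproduce. The check is calendar arithmetic and a comparison of sections.

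**Inputs.** Visit 5 is Day 360 ± 14 and visit 6 is Day 367 ± 10 (study calendar). The second bronchoscopy is at stage 2 visit 5 (section 5.5). One month is taken as 30 days (assumption). Withdrawal is taken to coincide with the last tablet and to end clinic visits (assumption; the plan does not say that early stoppers keep attending).

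**Step 1: the call date if *original* means scheduled visit 6.** For a stop on Day d, section 5.8 gives Day d + 30. Section 5.7 gives Day 367 + 30 = 397. The difference is 397 − (d + 30) = 367 − d.

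| Stop (Day d) | Call under 5.8 | Call under 5.7 | Difference (days) |
|---|---|---|---|
| 30 | 60 | 397 | 337 |
| 90 | 120 | 397 | 277 |
| 180 | 210 | 397 | 187 |
| 270 | 300 | 397 | 97 |

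For completers the rules nearly agree: 360 + 30 = 390 against 397, a difference of 7 days.

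**Step 2: the call date if *original* means the withdrawal date.** Section 5.7 then also gives about Day d + 30, and the difference is close to zero.

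**Step 3: what the AE form can capture.** Visits are nominally 90 days apart. A participant who withdraws on Day 80 has taken tablets for 80 days since Day 0, and the next form would have been due at Day 90. No early-termination visit is described, and the one-month call does not include the form. Whichever date section 5.7 means, the call as written adds nothing to section 9.4.

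**Step 4: how many people.** The plan states a 20% dropout rate, 0.20 × 72 = 14.4. It also expects 60 completers, 72 − 60 = 12. Hence 12 to 14 early stoppers. Fewer would be called, since section 5.7 covers only those who agree and the withdrawal reasons in section 5.6 include death.

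**Step 5: days covered after the second bronchoscopy.** Nominally visit 6 is 367 − 360 = 7 days after visit 5. At the extremes of the windows the gap can reach 377 − 346 = 31 days, and the windows overlap (Day 357 comes before Day 374). In the calendar as extracted, the last AE-form mark sits in the same column as the second-bronchoscopy mark. The last form may therefore fall on the day of the procedure or at visit 6. The number of days covered cannot be fixed.

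**The case against.** The strongest reply is that section 5.7 is a specific rule for early leavers and section 5.8 a general one. Keeping leavers on the completers' schedule is reasonable for a call about health and cancer status. That is a fair reading, but the text does not state it, and section 5.8 makes no exception.

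It can also be said that the timing of the call does no harm by itself: since the AE form is not completed then, moving the call changes no AE count. This is correct. Timing matters for safety only if the form is added, so the two parts of the fix belong together.

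Third, contact is not absent. Staff call within 24 and 72 hours of bronchoscopy, patients are told to report symptoms up to 30 days, completers are called at about Day 390 to 397, attributable Grade 2 or higher toxicity is followed to resolution, and IRB reporting has no end date. Section 7.4 sets no cut-off for DSMB review. This stands as partial cover. None of it, as written, requires the AE form to be completed, and the form is the stated source of the AE data.

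Three stronger readings are tempting and are not supported:

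- *The plan breaches its own 30-day risk windows.* The period in section 3.1, "from the time starting with the screening visit through 30 days after the last dose of study therapy", governs contraception, and the one in section 7.1.2.1 is an instruction to patients to call. Neither is an AE reporting window.
- *Recording stops 7 days after the second bronchoscopy, leaving 23 of 30 days uncovered.* The calendar does not settle this (step 5).
- *The safety comparison is biased toward no difference.* Both arms undergo the second bronchoscopy, so missed procedural events would be expected in both and mainly cause under-counting. For events linked to stopping tablets, such a bias is possible if symptoms on active treatment drive withdrawal, but the documents do not show it.

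**Conclusion.** The point holds as an unresolved conflict plus incomplete AE capture. If the date in section 5.7 is scheduled visit 6, the more natural reading, its call is later than that of section 5.8 by 97 to 337 days for stops between Day 270 and Day 30. A reader might infer that early stoppers will be called a year late. That is close to the maximum, reached only by those who stop in the first weeks, and it largely disappears on the other reading.

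Separately, and on either reading, AEs between an early stopper's last visit and stopping, or soon after the last tablet or second bronchoscopy, need not reach the section 9.4 comparison. The effect falls mainly on the 12 to 14 expected early stoppers among 72. Its direction between arms is not established. The conclusion rests on a 30-day month, on withdrawal ending clinic visits, and on the calendar's phone and mail columns carrying no AE form.

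**What to change.** 1. Give sections 5.7 and 5.8 one reference date for the call: each participant's actual last tablet or, for completers, the later of the last tablet and the second bronchoscopy.
2. Complete the AE Recording Form (Appendix 8) at that call, and show this in section 5.5 and the calendar.
3. Count the AEs collected there in section 9.4, alongside the existing 4 time points, and in the DSMB report under section 7.4.
4. If wanted, keep a later call timed from the scheduled off-study date for vital and cancer status.

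The cost is a wording change in these sections, about 12 to 14 extra short calls, and slightly more AE data to handle. Completers need no new contact, because their one-month call already exists.
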